	
Use of any of the following intracoronary medications is left to operator discretion as per site practice and/ or product instructions
 
 (i) Calcium Channel blockers (CCB): Verapamil/ Diltiazem (ii) Adenosine (iii) Nitroprusside 
Anti-thrombotics
 
Use of any of the following antithrombotic regimen is left to operator discretion as per site practice and/or product instructions
 
 (i) Heparin (ii) Bivalirudin (iii) Fondaparinux (iv) Group 2b/3a inhibitors e.g. eptifibatide (v) Cangrelor 
Pre-procedural preparation
 
 (i) For RCA/ dominant LCx lesions, operators can consider to standby atropine or temporary pacing wire (TPW) insertion if patient develops significant bradycardia/ cardiac conduction delays during the procedure 
Intracoronary imaging
 
 (i) The preferred intracoronary imaging platform is Intravascular Ultrasound (IVUS) i.e. Opticross or Opticross HD prior to intervention to evaluate target lesion characteristics and post-intervention to optimize stent expansion. However, the final selection is left to the discretion of the operators. (ii) Optical coherence tomography (OCT) is an alternative if deemed appropriate by the operators. 
Post-procedure
 
 (i) IV normal saline hydration based on clinical judgement to reduce risk of contrast induced nephropathy (CIN) (ii) If TPW was inserted but nil further brady-arrhythmia was noted, TPW can be safely removed prior to transfer out of cardiovascular laboratory (iii) To reduce post-procedural vasospasm, IV nitroglycerin can be administered
--	---

	
(iv) The subjects should receive dual antiplatelet therapy (DAPT) – one being that of aspirin and the other being a P2Y12 inhibitor – post- procedurally. The dose and duration of treatment is to be determined by the operator.
 
(v) All patients are recommended to be on DAPT for at least 6 months in duration post-PCI extendable to at least 12 months if they are deemed at low risk for bleeding.

Statistical analysis	
All analysis will be performed using SAS or STATA
 
Analysis will be conducted in two approaches, (1) according to the intention-to-treat (ITT) principle and (2) per-protocol analysis.

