3.3 Exit criteria

Participation in this study is optional and patients are free to withdraw their participation from this study at any time point during the study process without the need to provide any justification. Withdrawal from this study will not affect participants' future medical treatment.

Patients who have withdrawn their participation are not obligated to continue further follow-up and will not be replaced by new participants in this study. A reasonable sample size has been calculated to account for patient attrition.

Should the reason for withdrawal from the study be due to issues related to either safety or effectiveness of the study device, the investigator shall obtain a new separate consent from the subject, independent of the original study consent, to continue tracking his/her clinical progress/ situation.

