4.2 Study stages

4.2.1 Index visit: Within 48 hours of PCI

The following information will be captured during this index visit:

1. Demographics: Age, gender, ethnicity
2. Clinical characteristics: Clinical presentation (STEMI, NSTEMI, UAP, Angina, cardiac arrest), Symptoms (CCS angina score), Co-morbidities (diabetes mellitus, hypertension, hyperlipidemia, atrial fibrillation, smoking status, CKD/ ESRF, prior MI, prior PCI, prior CABG, prior CVA)
3. Laboratory results: full blood count, creatinine, electrolytes, fasting lipids/ glucose, HbA1c, cardiac injury markers i.e troponin T or I, CK, CK-MB)
 - a. If either troponin T or I is to be measured AFTER PCI with rotational atherectomy, a total of 3 sets are recommended at specific time intervals of 0-1 hours (1st set), 4-8 hours (2nd set) and 12-24 hours (3rd set) POST-PCI to ensure uniformity of sample collection across all sites.
 - b. Sites are to also provide the upper limit of normal values for their laboratory assay tests.
4. Medications: prior to PCI, during PCI, on discharge
5. ECGs (a post procedural ECG is required)
6. Echocardiographic data (LVEF)
7. Procedural data: Coronary anatomy (artery dominance, number of diseased vessels, presence of bypass grafts), target lesion (location by artery/grafts, proximal vs mid vs distal, branches (ramus, diagonal, OM, RPDA, graft)), rotational atherectomy (lubricant, burr size, run time, burr speed, number of passes, maximum rotational speed), adjunctive devices (guideliners, guide size, guide shape), PCI (type of PCI performed - POBA vs DEB vs DES, number of stents, pre and post-dilatation, stent overlap),

angiographic outcomes (TIMI flow, angiographic complications) procedural details (fluoroscopic duration, total contrast media)

8. Intravascular imaging data (OCT/ IVUS)
 - a. Sites will also send CDs of their angiograms and intravascular imaging
9. Outcomes data: Primary (residual stenosis in treated segment with TIMI 3 flow without mortality), Secondary (Death, periprocedural MI, complications (coronary perforation, no reflow, slow flow)
10. Primary operator data: ie. Operator initials (further anonymized prior to analysis), Age band, years of interventional cardiology practice, number of procedures. (PCI) performed preceding year (range), approximate number of rotablator performed last year (range)

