7.1 Primary efficacy endpoint

Procedural success defined as < 20% residual stenosis in treated segment without on-table mortality with TIMI 3 flow

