10.2 Statistical analysis of data set

Full analysis set (FAS): Refers to the set of analysis established in accordance to intention-to-treat (ITT) principle. All subjects who signed informed consent form and met all the inclusion criteria with the use of RA with or without other calcium debulking therapies will be included in this analysis. For subjects who are unable to complete the study follow-up, the primary endpoint will be based on the last observation carry forward method.

Per-protocol set (PPS): Refers to the set of analysis pertaining to the whole treated study population who have completed the study excluding those not fulfilling selection criteria or use of devices/ equipments not provided in this research study.

Safety analysis set (SS): Refers to all study subjects that have been evaluated at least once for safety outcome. Those with missing data will not be carried forward.

Efficacy analysis will be carried out based on the full analysis set and the per-protocol set.

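### The per-protocol set for procedural success depends on completing the study, although that endpoint is already fixed at the procedure and recorded within 48 hours

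*Protocol*

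**What the plan says.** **Analysis sets.** The Protocol synopsis (Statistical analysis) announces two approaches: "Analysis will be conducted in two approaches, (1) according to the intention-to-treat (ITT) principle and (2) per-protocol analysis". Section 10.2 defines the PPS as "the set of analysis pertaining to the whole treated study population who have completed the study", and then removes patients who fail the selection criteria or were treated with certain devices. It adds: "Efficacy analysis will be carried out based on the full analysis set and the per-protocol set".

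**Completion.** The section does not define it. The nearest guide is the FAS paragraph just before, which has a rule that begins "For subjects who are unable to complete the study follow-up" and keeps those patients in by carrying the last observation forward. The only scheduled contact after the index visit is the 12-month telephone call (synopsis, Follow-up; section 4.2.2), supplemented by a review of medical records at 12 months (note to the data collection schedule).

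**Endpoint.** Section 7.1 gives the primary efficacy endpoint as "Procedural success defined as < 20% residual stenosis in treated segment without on-table mortality with TIMI 3 flow". Section 4.2.1, headed "Index visit: Within 48 hours of PCI", lists among the items captured then: "Outcomes data: Primary (residual stenosis in treated segment with TIMI 3 flow without mortality". Section 4.2.2 lists the 12-month outcomes, and procedural success is not one of them.

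**Withdrawal.** Section 3.3 says: "Patients who have withdrawn their participation are not obligated to continue further follow-up and will not be replaced".

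**The concern.** Nothing collected after the index visit can change whether a procedure succeeded. Yet membership of one of the two sets in which success is estimated appears to depend on what happens over the following year. A patient with a clean procedural result who withdraws at month 3 or cannot be reached at month 12 would count in the FAS and not in the PPS.

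Two things are at stake. The first is precision in the PPS, because recorded results are set aside. The second is interpretation. A per-protocol estimate is normally read against the full-set estimate to see whether departures from the protocol matter. If the sets also differ by 12-month retention, a gap between them cannot be put down to how the procedure was done, and the lack of a gap is equally hard to read.

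**Working it through.** **Step 1. Timing.** Residual stenosis, TIMI flow and on-table death (section 7.1) are all known when the procedure ends. They are recorded within 48 hours (section 4.2.1). Completion, read as end of follow-up, is known at 12 months. So the condition for entering the PPS comes after the endpoint.

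**Step 2. The plan's own figures.** Sections 10.1.2 and 10.1.3 use a 5% complication rate, a 95% interval of total width 3%, up to 20% dropout and a final 1000 subjects. The asymptotic formula gives N = (2 × 1.96)² × 0.05 × 0.95 / 0.03² = 811 after rounding up, which matches Table 1. Allowing for 20% dropout, 811/0.8 = 1014 and 811 × 1.2 = 974; the stated 1000 lies between them. The sample size rests on the complication rate and is not affected by this point.

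**Step 3. Results set aside.** With N = 1000 and non-completion d, the number is 1000 × d: 200 at d = 0.20 (the ceiling in 10.1.2), 100 at 0.10 and 50 at 0.05. The two lower values are assumptions.

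**Step 4. Precision.** The protocol gives no expected success rate, so p = 0.90 is assumed. The half-width is 1.96 × √(p(1 − p)/n) = 1.96 × √(0.09/n).

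**Step 5. Possible shift.** Let failures be lost at k times the rate of successes, with overall loss d. The loss rate among successes is r = d / (p + (1 − p)k), and success in the PPS is p(1 − r)/(1 − d). For d = 0.20 and k = 2: r = 0.20/1.10 = 0.1818, and 0.90 × 0.8182/0.80 = 92.05%. For k = 0.5: r = 0.20/0.95 = 0.2105, and 0.90 × 0.7895/0.80 = 88.82%. The values of k are assumptions.

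| d | n left | Half-width (points) | PPS success, k = 0.5 | k = 1 | k = 2 |
|---|---|---|---|---|---|
| 0 | 1000 | 1.86 | 90.00% | 90.00% | 90.00% |
| 0.05 | 950 | 1.91 | 89.75% | 90.00% | 90.43% |
| 0.10 | 900 | 1.96 | 89.47% | 90.00% | 90.91% |
| 0.20 | 800 | 2.08 | 88.82% | 90.00% | 92.05% |

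**Step 6. Sensitivity to p.** At d = 0.20 and k from 0.5 to 2, PPS success runs from 77.78% to 83.33% for p = 0.80, and from 94.39% to 96.13% for p = 0.95.

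**The case against.** The case for leaving the text alone has several parts.

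- **The FAS carries the result.** It has no completion condition. Section 10.4 plans only a proportion with a 95% interval, and no threshold, test or rule on agreement between the sets depends on the PPS. This stands, and it is why the point is minor.
- **Completion is undefined and could be settled elsewhere.** The 12-month record review may let a patient who was not reached count as complete. Death at one year is itself a study outcome, so a patient who dies may also count as complete. This stands too: the figure of 200 is an upper limit on one reading, not a certain loss.
- **Requiring completion in one study-wide per-protocol set is common**, and willingness to comply with follow-up is an inclusion criterion. That is fair for 12-month outcomes. It does not explain why an endpoint known on the day should depend on it, and section 10.2 ties the PPS specifically to efficacy.

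A reader might infer more than the documents support in two ways.

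- **Inflated success.** One might say the PPS will overstate success because failures drop out more. The protocol gives no completion rate by procedural result, and the shift can be negative, nil or positive.
- **On-table deaths.** One might say the PPS removes on-table deaths, which are failures by definition. If 0.6% of patients were consented on-table deaths, success would move from 90% to 0.90/0.994 = 90.54%. But 0.6% is the all-death rate in the three largest series of Appendix 1 and is not stated to be on-table. The data collection schedule and section 4.2.1 place consent at the index visit, and the Figure 6 caption puts unexpected deaths in the stream without consent. On those passages no on-table death enters either set. Section 11.5 requires consent before inclusion, and the synopsis enrols at the point of treatment, so the timing is not fully settled. Zero is plausible, and the 0.54 points should not be used as an effect size.

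**Conclusion.** The point holds as a minor one. Section 10.2 makes the PPS conditional on study completion, while procedural success is determined at the procedure and recorded within 48 hours. If completion means the 12-month follow-up, known results leave the PPS for reasons that arise after the endpoint. The loss is at most 200 of 1000, and fewer if record review or death counts as completion.

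At an assumed 90% success rate, the half-width grows by at most 0.22 points (1.86 to 2.08). The shift lies between -1.2 and +2.0 points for assumed loss ratios of 0.5 to 2, and is zero if losses are unrelated to the procedural result. The documents support neither a direction of bias nor any effect on the FAS. What remains is that a difference between the two sets could reflect retention and be read as adherence.

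**What to change.** Add one sentence to section 10.2, for example: *For procedural success, the study-completion condition does not apply; treated patients with a recorded procedural result, including on-table death where consent was given, remain in the per-protocol set whatever their 12-month status.*

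Keep the other PPS exclusions (selection criteria and devices). Replacing the whole definition with all consented, eligible, treated patients who have a result would nearly reproduce the FAS, and the comparison would then say nothing about adherence. The completion condition can stay for 12-month outcomes if it is wanted there, in which case it should be defined, including how deaths and patients traced only through records are classed.

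The cost is one sentence. No new data are needed, because the result is already an index-visit item.

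Separately, the device exclusion can be read as devices not supplied by the study or devices not foreseen by it, while the synopsis and sections 6.3 and 6.4 leave much of the equipment choice to the operator. That wording could be clarified in the same edit, but it adds no weight to this point.

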10.3 Statistical analysis plan

All demographic data, clinical characteristics, laboratory results, medications, electrocardiography, imaging, angiographic data, intravascular data, outcomes, primary operator data and hospital data will be analyzed. Continuous variables will be described using mean, median, standard deviation, interquartile range (IQR) and minimum/maximum values. Discrete variables will be described using frequency tables. A t-test will be used to assess if there is a significant difference ($p<0.05$) in continuous data and a chi-square test will be used in discrete data.

All statistical comparisons will be performed using two-sided tests with a significance level of 0.05. Statistical analysis will be performed using STATA or SAS software.

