10.1.2 Assumptions

The target sample size is calculated based on the following assumptions:

1. The proportion of RA-related complications is 5%
2. 95% confidence intervals width is 3%.
3. Up to 20% of patients are assumed to drop out of this study

Sample							
Confidence	Size	Target	Actual	Proportion	Lower	Upper	Width if
Level	(N)	Width	Width	(P)	Limit	Limit	P = 0.5
0.95	1118	0.02	0.02	0.03	0.02	0.04	0.059
0.95	1476	0.02	0.02	0.04	0.03	0.05	0.051
0.95	1825	0.02	0.02	0.05	0.04	0.06	0.046
0.95	2167	0.02	0.02	0.06	0.05	0.07	0.042
0.95	497	0.03	0.03	0.03	0.015	0.045	0.088
0.95	656	0.03	0.03	0.04	0.025	0.055	0.077
0.95	811	0.03	0.03	0.05	0.035	0.065	0.069
0.95	963	0.03	0.03	0.06	0.045	0.075	0.063
0.95	280	0.04	0.04	0.03	0.01	0.05	0.117
0.95	369	0.04	0.04	0.04	0.02	0.06	0.102
0.95	457	0.04	0.04	0.05	0.03	0.07	0.092
0.95	542	0.04	0.04	0.06	0.04	0.08	0.084

Table 1: Numeric Results for Two-Sided Confidence Intervals for One Proportion Confidence Interval

Formula: Simple Asymptotic

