10.6 Safety evaluation

Kaplan-Meier curve will be used to construct 1-year cumulative event rates with 95% confidence interval.

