10.7 Sub-group analysis

This study will collect all subjects who have undergone calcium debulking therapy and evaluate real-world clinical outcomes

The following sub-groups (but not limited to) may be utilised for analysis:

- (i) Acute coronary syndrome
- (ii) Lesion length
- (iii) Bifurcation lesions
- (iv) Multiple overlapping stents (≥ 2 stents for each epicardial coronary artery)
- (v) Chronic kidney disease

- (vi) Multivessel disease (\geq 2 vessel CAD)
- (vii) Left main (LM) equivalent
- (viii) Chronic total occlusions (CTO)
- (ix) Severely impaired LVEF i.e. \leq 30%
- (x) IVUS subgroup

11 Study Management

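### Section 10.3 makes chi-square the test for all discrete data without exempting the 1-year events, so as written a between-group comparison of those events would use a test that cannot handle censoring (minor)

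*Protocol*

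**What the plan says.** Four sections of the protocol bear on this.

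- **10.3** is a general paragraph on everything collected. Its list ends with "intravascular data, outcomes, primary operator data and hospital data will be analyzed". It then assigns a t-test to continuous data and states that "a chi-square test will be used in discrete data". A closing rule covers every comparison: "All statistical comparisons will be performed using two-sided tests with a significance level of 0.05". These are the only two tests named in the protocol; log-rank and Cox regression do not appear.
- **10.6** handles the 1-year events as time-to-event data: "Kaplan-Meier curve will be used to construct 1-year cumulative event rates with 95% confidence interval". It names no test for comparing curves. The events, listed in 8.2 (Safety index), include death, MI, target lesion revascularisation, stent thrombosis, MACE and stroke.
- **10.7** sets out ten subgroups, all optional: "The following sub-groups (but not limited to) may be utilised for analysis". It attaches no endpoint and no test to them.
- **10.1.2** expects incomplete follow-up: "Up to 20% of patients are assumed to drop out of this study". For the safety set, 10.2 adds "Those with missing data will not be carried forward".

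**The concern.** The 1-year events are yes/no outcomes, and 10.3 covers outcomes without qualification. Someone following 10.3 literally would compare 1-year MACE between, say, patients with and without chronic kidney disease by a chi-square test on a two-by-two table. Such a table forces a choice for each patient lost before 12 months without an event: count as event-free, or leave out. Kaplan-Meier does neither; it uses the patient up to the time of loss. The p-value and the curve beside it would then rest on different data and could disagree.

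The protocol does not say which coding the chi-square test would use. That leaves a choice open after the data are seen, on an outcome belonging to study aim 4 (clinical outcome after rotational atherectomy).

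**Working it through.** **The plan's own figure.** The protocol gives no figure for group comparisons. Its one calculation, in 10.1, is the precision of a single proportion: n = 4 × 1.96² × 0.05 × 0.95 / 0.03² = 811, which matches Table 1. Allowing for 20% drop-out, 811 / 0.80 = 1014, close to the stated 1000. None of this depends on the test discussed here.

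**Inputs.** From the protocol: 1000 patients, up to 20% drop-out, two-sided 0.05, 12 months of follow-up for all. Assumed, because the protocol is silent: two groups of 500, 1-year risk r = 15%, constant hazard, drop-out times uniform over the year, drop-out d = 30% v 10% (mean 20%).

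**Step 1: what the table would show when the true risk is 15% in both groups.** The hazard is λ = −ln(0.85) = 0.1625. A drop-out has an event before leaving with probability m = 1 − r/λ = 1 − 0.15/0.1625 = 0.077. The observed event proportion is p = (1 − d)r + d·m.

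- d = 30%: 0.70 × 0.15 + 0.30 × 0.077 = 0.128
- d = 10%: 0.90 × 0.15 + 0.10 × 0.077 = 0.143

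If drop-outs without an event are removed, the denominator becomes p + (1 − d)(1 − r).

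- d = 30%: 0.128 / (0.128 + 0.595) = 0.177
- d = 10%: 0.143 / (0.143 + 0.765) = 0.157

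Equal true risks thus appear as 12.8% v 14.3% under one coding and 17.7% v 15.7% under the other. The biases run in opposite directions.

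**Step 2: type I error.**

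- Drop-outs event-free: SE = √(0.1354 × 0.8646 × 2/500) = 0.0216, shift = 0.0146/0.0216 = 0.67, rejection = Φ(−1.96 + 0.67) + Φ(−1.96 − 0.67) ≈ 10%.
- Drop-outs removed (about 362 v 454 patients left): SE = √(0.1661 × 0.8339 × (1/362 + 1/454)) = 0.0262, shift = 0.0200/0.0262 = 0.76, rejection ≈ 12%.

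Simulations of 3000 to 4000 runs agree: 9.5% to 10.5% and 11.6% to 12.2%, with log-rank at 5.0% to 5.2%.

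**Step 3: power when the true risk is 20% v 15%, with the 30% drop-out in the higher-risk group.** For r = 20%, m = 1 − 0.20/0.2231 = 0.104.

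- Event-free: p = 0.70 × 0.20 + 0.30 × 0.104 = 0.171 v 0.143; shift = 0.0284/0.0230 = 1.24; power ≈ 23% to 24%.
- Removed: 0.171/(0.171 + 0.560) = 0.234 v 0.157; shift = 0.0768/0.0277 = 2.78; power ≈ 79% to 80%.
- Log-rank (simulation): 50% to 52%.

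The 80% is no gain. Part of it is the same upward bias that produces the 12% false-positive rate in step 2.

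**Step 4: how far this depends on the assumptions.** Type I error unless stated:

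| Scenario | Chi-square, event-free | Chi-square, removed | Log-rank |
|---|---|---|---|
| 500 v 500, risk 15%, drop-out 35% v 5% | about 17–19% | about 21% | about 5% |
| 500 v 500, risk 15%, drop-out 22% v 18% | 5.2% | 5.5% | 5.0% |
| 300 v 700, risk 5 / 10 / 20%, drop-out 35% v 13.6% | 6.3 / 7.6 / 14.7% | 7.6 / 10.6 / 12.9% | 4.7 / 4.3 / 5.5% |
| 300 v 700, risk 5 / 10 / 20%, drop-out 20% in both | 6.0 / 5.3 / 5.0% | 5.8 / 5.4 / 4.9% | 5.8 / 5.3 / 5.1% |
| 300 v 700, 15% v 9%, drop-out 20% in both (power) | 74.3% | 73.9% | 74.4% |

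The first four rows have no true difference. With equal drop-out in 300 v 700 patients and no true difference, chi-square (event-free) and log-rank reach different verdicts in only about 1% of runs.

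**The case against.** The strongest reply is that no sentence in the protocol says subgroup comparisons of 1-year events will use chi-square. A reader might infer that they will, and that the analysis therefore ignores censoring. The text does not support that as a statement of fact: 10.3 is general, 10.6 is the specific section and treats these events as time-to-event data, and 10.7 is optional and assigns neither endpoint nor test. The test that goes with a Kaplan-Meier curve is also commonly left to a statistical analysis plan, so the mere absence of log-rank or Cox is not an error. All of this stands. It does not remove the point that 10.3 makes a positive choice of test, includes outcomes, and then speaks for all comparisons without exempting the 1-year events.

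A reader might also infer that chi-square simply loses power, 24% against about 51%. That holds only if drop-outs are counted event-free. With drop-outs removed, which the no-carry-forward rule in 10.2 makes at least as likely, the same scenario gives about 80%. The defect is an undefined and biased comparison, not a loss of power in one direction.

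Finally, the size rests on assumptions. The protocol gives no drop-out by subgroup, and mild imbalance does no visible harm. Timing matters too: follow-up is one telephone contact at 12 months plus a record review. If a lost patient contributes nothing after the index stay, chi-square with drop-outs removed matches log-rank (type I error 5.6% v 5.4% at 30% v 10% drop-out; power 45.9% v 45.5%). This limits the severity.

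**Conclusion.** The point holds as a minor one: the chi-square rule in 10.3 is drawn too broadly and sits badly with the Kaplan-Meier estimation in 10.6. Under equal drop-out the consequence is negligible. Under markedly unequal drop-out spread over the year, the false-positive rate could roughly double, and the answer would depend on a coding choice that the protocol does not fix for this test. Whether that would occur in this registry cannot be judged from the protocol. The procedural success rate, the rotational-atherectomy complication rate, the 48-hour and 1-year single-cohort estimates and the sample size are all untouched.

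**What to change.** In 10.3, limit the chi-square test to baseline and procedural variables and to outcomes fixed by 48 hours. In 10.6 or 10.7, add a sentence such as: Any between-group comparison of 1-year events uses the log-rank test and/or a Cox model, on the same event and censoring times as the Kaplan-Meier estimates.

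The cost is a short edit to the analysis section. No new data are needed, because the Kaplan-Meier estimates already require event and censoring times.

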Sub-group analysis	
This study will evaluate real world clinical outcomes of all enrolled patients who have undergone calcium debulking therapies. The following sub-groups listed below (but are not limited to) may be used for further analysis:
 
 (i) Acute coronary syndrome (ii) Lesion length (iii) Bifurcation lesions (iv) Multiple overlapping stents (≥ 2 stents for each epicardial coronary artery) (v) Chronic kidney disease (vi) Multivessel disease (≥ 2 vessel CAD) (vii) Left main (LM) equivalent (viii) Chronic total occlusions (CTO) (ix) Severely impaired LVEF i.e. $\leq 30\%$ (x) IVUS subgroup
Primary site	National Heart Centre Singapore (NHCS)

Study flow chart

Data collection schedule

	Baseline	Follow-up
Time	≤ 48h after PCI	12m
Visit timeline	V _{start}	V _{end}
Informed consent	X	
Entry criteria	X	
History / demographic data	X	
Symptoms (CCS score)	X	X
Laboratory [^]	X	
DAPT use data*		X
Adverse events recording	X	X

Note:

Laboratory testing: full blood count, liver function (ALT, AST), renal function (BUN, creatinine), lipids (total cholesterol, LDL cholesterol, HDL cholesterol, triglycerides), glucose, coagulation panel (APTT/PT), myocardial injury markers include: CK, CK-MB, TnT / TnI.etc.

* DAPT recommendations may differ based on clinical situation/ stent use. Data collected will be type of antiplatelets and recommended duration for each antiplatelets used.

Note: All subjects will be followed up 12 months post PCI via telephone consult to check on symptoms, compliance, and development of adverse events. Medical records will also be reviewed at the end of 12 months for any clinically significant events.

Table of Contents

1. Research background -----	15
1.1 Introduction to disease-----	16
1.1.1 Disease Profile -----	16
1.1.2 Epidemiology and risk factors -----	16
1.1.3 Pathophysiology and classification -----	16
1.1.4 Detection of CAC -----	16
1.2 Introduction to treatment-----	17
1.2.1 Rotational atherectomy-----	17
1.3 Introduction to equipment-----	17
1.3.1 Structure and basic principle of ROTABLATOR™-----	17
1.3.2 Principle-----	19
2. Study Aim -----	20
3. Selection and exit criteria -----	20
3.1 Inclusion criteria-----	20
3.2 Exclusion criteria-----	21
3.3 Exit criteria-----	21
3.4 Early termination -----	21
3.4.1 Study termination criteria -----	21
3.4.2 Study site termination criteria -----	22
4. Study design-----	22
4.1 Research design-----	22

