1.3.2 Principle

RA ablates using a diamond-encrusted elliptical burr which rotates at speeds of 140,000 – 180,000 rpm driven by a helical draft shaft that is advanced across a lesion over a guidewire. The burr causes “differential cutting” and preferentially ablates hard, inelastic, calcified plaques that are unable to stretch away from the RA burr compared to healthy arterial tissue (Figure 5). While RA has been shown to selectively remove calcium deposits, IVUS studies have also shown that adjacent endothelial cells may be abraded during the process leading to vasospasm²⁸. However, high speed RA generally generates low friction during the creation of smooth lumen-atheroma interface with incidence of coronary artery dissection significantly lower than balloon

angioplasty alone²⁸. On the other hand, low speed RA tend to cause fissures and debris formation between plaque and membrane, creating an irregular wall in the process.

[figure not shown]

Figure 5: Differential cutting of ROTABLATOR™. Source: Barbato et.al. 2017

At rotational speed of 160,000 to 200,000 rpm, the RA burr head will pulverize atherosclerotic plaque into granules. Studies have found that a vast majority of the particles produced during atherectomy have a < 10-15 μ m size which will be cleared by the phagocyte system. It does not cause capillary thrombosis nor negatively affect left ventricular function. Despite this, the heat generated during the forward grinding can lower rotational speed with possibility of generating larger particles especially when the rotational speed drops below 75,000 rpm.

2. Study Aim

- 1 To describe the use of RA in real world practice in Asia
- 2 To determine predictors of procedural success
- 3 To determine predictors of major procedural complications: perforation and no-reflow phenomenon
- 4 To assess the clinical outcome of patients undergoing RA for heavily calcified coronary lesions.

3. Selection and exit criteria

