4.2.2 Follow-up at 12 months: telephone contact

The following information will be captured during this 12-month follow-up visit: Symptoms (CCS score), medications (antiplatelet therapy, statins, non-statins LDL lowering therapy), outcomes (death, MI, TLR, stent thrombosis, and stroke).

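### If CCS angina class is tested, the chi-square rule in section 10.3 does not suit an ordered grade taken twice in the same patients (minor)

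*Protocol*

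**What the plan says.** Protocol section 10.3 commits to analysing all the main groups of collected data, including clinical characteristics and outcomes, and then names two tests. For continuous data, "A t-test will be used to assess if there is a significant difference". For the rest, "a chi-square test will be used in discrete data". The level is common to all: "All statistical comparisons will be performed using two-sided tests with a significance level of 0.05". Nothing in section 10 names a method for ordered categories or for repeated readings, and the t-test is not said to be paired or unpaired.

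CCS class is collected twice. Section 4.2.1 lists "Symptoms (CCS angina score") among the clinical characteristics at the index visit. Section 4.2.2 lists it again for the 12-month call: "Symptoms (CCS score), medications (antiplatelet therapy, statins, non-statins LDL lowering therapy), outcomes (death, MI, TLR, stent thrombosis, and stroke"). The data collection schedule in the synopsis marks it at both times, and it is the only graded scale so marked. It bears on the fourth aim in section 2: "To assess the clinical outcome of patients undergoing RA for heavily calcified coronary lesions".

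CCS is not among the primary, secondary or safety endpoints in sections 7 and 8. Sections 10.4 to 10.6 plan rates with confidence intervals and Kaplan-Meier curves. Section 10.7 lists ten subgroups that may be used, without tying any of them to a particular outcome.

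**The concern.** A grade with a few levels is most naturally read as discrete, and 10.3 then sends it to a chi-square test. Two properties of CCS are lost.

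- **Order.** The test treats the classes as unordered labels. A general drift to lower classes is spread over several degrees of freedom instead of being concentrated in one.
- **Pairing.** In its usual form the test treats a patient's baseline and 12-month readings as coming from two different people, so the variance is wrong for a before-after comparison.

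At stake is a symptom result that could miss a modest improvement, or a difference between subgroups, that the registry's own data would show. The primary, secondary and safety results are not touched.

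**Working it through.** **1. Number of patients.** Section 10.1.2 assumes a 5% complication rate, a 95% interval of full width 3% and up to 20% dropout. The plan's own figure reproduces:

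n = (2 × 1.96)² × 0.05 × 0.95 / 0.03² = 811, as in Table 1.

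Allowing for dropout, 811 / 0.8 = 1014 and 811 × 1.2 = 974, so the stated 1000 is reasonable. It leaves 1000 × 0.8 = 800 patients with a 12-month reading. This sample size rests on interval width for complications and is unaffected by the CCS point.

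**2. Why the unpaired test is conservative.** For the share p in any class with no change, the variance of the before-after difference is [2p(1 − p) − 2c] / n, where c is the within-patient covariance. The unpaired chi-square uses 2p(1 − p) / n. With c > 0 its variance is too large, so it rejects too seldom. With five classes at two times it also has (2 − 1) × (5 − 1) = 4 degrees of freedom, where a test of ordered shift needs one.

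**3. Before-after comparison, simulated.** The protocol gives no CCS distribution, correlation or effect, so all of these are assumptions. CCS was generated as a latent normal score cut into five classes, with a shift in SD units and a within-patient correlation r. Tests are two-sided at 0.05.

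Baseline shares 10/25/40/20/5%, 1500 runs per scenario:

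| Pairs | Shift (SD) | r | Unpaired chi-square | Signed-rank |
|---|---|---|---|---|
| 80 | 0.30 | 0.3 | 23.0% | 54.7% |
| 80 | 0.30 | 0.5 | 17.3% | 67.4% |
| 800 | 0.15 | 0.3 | 62.3% | 90.9% |
| 800 | 0.15 | 0.5 | 62.0% | 96.4% |

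With no change, the unpaired chi-square rejected in 2.0-3.5%. At 0.3 SD or more in all 800, both tests reached about 100%.

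Baseline shares 15/25/35/18/7%, 800 pairs, 2000 runs per scenario:

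| Shift (SD) | r | Unpaired chi-square | Signed-rank |
|---|---|---|---|
| 0 | 0.3 | 3.6% | 4.4% |
| 0 | 0.5 | 2.5% | 5.0% |
| 0 | 0.7 | 1.3% | 5.1% |
| 0.10 | 0.3 | 26.0% | 62.0% |
| 0.10 | 0.5 | 22.3% | 72.1% |
| 0.20 | 0.3 | 91.4% | 99.4% |
| 0.20 | 0.5 | 93.7% | 99.95% |
| 0.50 | 0.3 to 0.7 | 100% | 100% |

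Order and pairing both contribute. At r = 0.5 and 0.10 SD, an unpaired rank test (order kept, pairing ignored) has 46.6% power, between 22.3% and 72.1%.

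**4. 12-month CCS between subgroups, simulated.** 800 patients, proportional-odds ratio 1.6, three assumed class distributions, 3000 runs each. With 25% of patients (800 × 0.25 = 200) in the subgroup:

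| 12-month shares, classes 0 to IV (%) | Chi-square | Rank-sum | Gain (points) |
|---|---|---|---|
| 60/20/13/5/2 | 69.9% | 85.4% | 15.5 |
| 75/13/8/3/1 | 59.2% | 78.1% | 18.9 |
| 40/30/20/8/2 | 74.0% | 89.2% | 15.2 |

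For a 10% subgroup (80 patients) the ranges are 38-44% and 50-60%. At an odds ratio of 1 both tests reject in about 5%, so only power is at issue here.

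**The case against.** The strongest reply is that the protocol plans no CCS comparison at all. CCS is missing from every endpoint list, section 4.2.2 lists it apart from the outcomes, no baseline-to-12-month test of any variable is named, and the subgroups are optional. This stands. A reader might infer that a planned symptom outcome is compromised; the document does not support that, and the harm is conditional on CCS being tested.

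A second reply is that the protocol never calls CCS discrete. It calls it a score, which could go to the t-test, and an unspecified chi-square test could include McNemar-type or trend versions. It is true that the classification is an inference. The t-test route does not clearly help, because 10.3 does not say the t-test is paired. Under similar assumptions an unpaired t-test rejected in only 1-2% with no change, and with 80 pairs and a 0.3 SD shift it had 39-43% power against 54-67% for the signed-rank test.

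A third reply is that such detail belongs in a separate SAP, which could refine the rule. But 10.3, itself headed as the statistical analysis plan, does not leave the test open. It fixes one without an exception for ordered or repeated data.

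Finally, this is a single-arm registry whose baseline column is timed within 48 hours after PCI, so a before-after p-value could not be attributed to atherectomy under any test. That also stands, and it limits how much the point matters.

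**Conclusion.** The point holds as a minor one. The only test that 10.3 gives for discrete data ignores the order of CCS classes and, in its usual form, the pairing of the two readings. It affects the symptom result only if CCS is tested.

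Two stronger readings are not supported. One is that the error rate is wrong in a harmful direction. The before-after chi-square is conservative (about 1.5-4% rejection under no change at assumed correlations of 0.3 to 0.5), and between subgroups the level is correct. The other is that power is lost generally. The loss is large for small shifts and in subgroups, at most about 8 points at 0.20 SD in 800 pairs (91.4% against 99.4% at r = 0.3), and little or none from about 0.3 SD. Between subgroups it is about 15-19 points at an odds ratio of 1.6 and a 25% share.

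All CCS distributions, correlations, shifts and odds ratios are assumed. The between-subgroup gain was computed for the rank-sum test; the gain from a baseline-adjusted proportional-odds model was not.

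**What to change.** In section 10.3, add:

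> Ordinal variables, including CCS class, will be analysed with their order kept: change from baseline to 12 months by the Wilcoxon signed-rank test in patients with both readings, and any subgroup comparison of 12-month CCS by a Wilcoxon rank-sum test or a proportional-odds model adjusted for baseline CCS. The chi-square test is kept for unordered, independent categories.

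Report beside the result how many patients died or were not reached, since the comparison covers only those with both readings. If no CCS test is intended, a sentence saying that CCS is descriptive only would also settle the matter.

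The cost is two sentences and no new data, visits or patients. The one downside is a routine check of the proportional-odds assumption if that model is used.
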